#### 4.3 ANALYSIS OF THE SECONDARY EFFICACY ENDPOINT(S)

Six secondary outcomes are of interest in this trial. We will use a fallback method to control for type I error (see page 30 of the Food and Drug Administration guidance on multiple endpoints in clinical trials; <https://www.fda.gov/regulatory-information/search-fda-guidance-documents/multiple-endpoints-clinical-trials-guidance-industry> ). More specifically, these secondary outcomes will only be formally tested if the primary hypothesis was rejected at level alpha=0.05. If the study stops without the CE30 test statistic crossing the 'efficacy boundary' or 'futility boundary' (i.e. not enough primary endpoint events), the key secondary endpoints will be evaluated and summarized using point estimates and associated 95% confidence intervals (without p-values).

The ordering of the secondary endpoints is as follows:

- 1) Composite endpoint of mortality and EQ5D index at Day 30 (QOL&M30)
- 2) Composite endpoint of mortality and EQ5D index at Day 90 (QOL&M90)
- 3) Primary endpoint at 45 days (CE45)

- 4) Primary endpoint at 90 days (CE90)
- 5) Venous events at 30 days (CEVTE30)
- 6) Arterial events at 30 days (CEATE30)

Using a fallback method the 0.05 type I error rate would be split as follows – 0.025, 0.005, 0.005, 0.005, 0.005, and 0.005. If QOL&M30 was statistically significant then QOL&M90 would be tested at  $0.03 = 0.025 + 0.005$ . On the other hand, if QOL&M30 was NOT statistically significant then QOL&M90 would be tested at 0.005. The process would continue until all 6 secondary endpoints were tested. If the study does not accumulate enough CE30 events, it is expected that there would be limited information for secondary endpoints 3-6.

Statistical methods for testing the QOL&M30 and QOL&M90 endpoints will be based on a proportional odds model. The covariates in the model will include the participant's age (restricted cubic spline with 3 knots), sex, D-dimer (normal or abnormal), BMI (restricted cubic spline with 3 knots), antiplatelet usage (yes/no - at enrollment), WHO severity score (<five vs.  $\geq$ five), and the randomized treatment. The results of these models will be summarized using an odds ratio and associated 95% confidence interval.

Secondary analyses of the QOL&M30 and QOL&M90 endpoints will use a multiple imputation approach. 20 datasets will be imputed using predictive mean matching and the above covariates plus the Day 2 and Day 90 EQ5D index scores. The model estimates will be combined using Rubin's rules to obtain the estimated odds ratio and 95% confidence interval.

Statistical methods for testing the secondary endpoints 3-6 listed above will follow the same procedures used for the primary endpoint described in Section 4.2 above. Except that for the CEVTE30 and CEATE30 events, an additional sensitivity analysis will be conducted by combining death from any causes to each one of the events separately.

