The study period is 90 days, with follow-up assessments on days 2, 10, 20, 30, 45, and 90 days from randomization. The initial follow-up encounter, which will be conducted by the Call Center via the participant's preferred method (electronic or phone call), will occur within 2 days following discharge from the hospital, to confirm study medication adherence and perform an initial assessment of outcomes. Subsequent encounters, which will also be conducted by the Call Center electronically or by phone, will occur at 10, 20, and 30 days after enrollment. With each encounter, assessments of medication adherence and outcomes will be performed. Two additional encounters will occur after completion of the primary outcome, at 45 and 90 days after enrollment, to determine if there is an increased risk for thromboembolic complications following hospital discharge that extends for a longer period than 30 days and to facilitate/confirm collection of the 2nd set of biorepository specimens.

This first stage of the ACTIV-4C trial uses a group-sequential design where interim analyses are planned to assess the efficacy and futility of the treatments with the potential for early stopping. Proper statistical approaches are used to control type I error at the interim and final analyses. Safety monitoring will be performed throughout the trial and will be periodically reported by the Data and Safety Monitoring Board (DSMB) established for ACTIV-4C which will have oversight responsibility for the study.

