#### 3.2 KEY SECONDARY AND EXPLORATORY ENDPOINTS

Key secondary endpoints include the following.

1. The composite endpoint of EQ5D index score and mortality at day 30 following randomization
2. The composite endpoint of EQ5D index score and mortality at day 90 following randomization
3. The composite endpoint for the primary outcome at day 45 following randomization
4. The composite endpoint for the primary outcome at day 90 following randomization
5. Composite endpoint of venous thromboembolic events, including symptomatic DVT of the upper or lower extremities, symptomatic and/or clinically relevant PE, and other symptomatic venous thrombosis, including cerebral sinus and splanchnic vein thrombosis at day 30
6. Composite endpoint of arterial thromboembolic events, including symptomatic ischemic stroke, myocardial infarction, and other symptomatic arterial thromboembolic events at day 30

Secondary endpoints will be formally tested using a fallback approach (see Section 4.3) only if the primary endpoint was statistically significant at the two-sided 5% level.

Exploratory endpoints include the following.

1. All-cause mortality at day 30 following discharge from the hospital
2. All-cause re-hospitalization at day 90 following discharge from the hospital

Table 1. Summary of important questions of interest and related estimands

Row	Question of Interest	Objective Description / Study Population	Endpoint	Intercurrent Events/Strategy to handle	Population Summary Estimands
1	Does Apixaban reduce the rate of venous and arterial thromboembolic outcomes, and all-cause mortality during 30 days after discharge?	Primary Objective of the Study / All Randomized Participants	Composite endpoint (CE) of venous and arterial thrombotic complications—including new, symptomatic proximal, or distal DVT of the upper or lower extremities, PE, and new thrombosis of other veins (including cerebral sinus and	The only intercurrent event will be patient drop-out. The drop-out is expected to be less than 5% and un-related to treatment and their data up to the time of drop-out will be	The difference in the proportion of CE between the Apixaban arm and the placebo arm. A negative value will favor the

			splanchnic veins), ischemic stroke, myocardial infarction, other arterial thromboembolism (e.g., mesenteric or acute limb ischemia), and all-cause mortality by day 30	used in the event determination*	Apixaban arm.

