### 3.5 POWER AND SAMPLE SIZE

The primary analysis for this randomized trial will be an intention-to-treat comparison of a composite endpoint (CE) of venous thromboembolic events, including new, symptomatic proximal or distal deep vein thrombosis affecting the upper and/or lower extremities, pulmonary embolism, or thrombosis of other veins (e.g., cerebral sinus veins, splanchnic veins); arterial thromboembolic events, including new ischemic stroke, myocardial infarction, mesenteric or peripheral arterial thromboembolism; and all-cause mortality for up to 30 days after randomization across the intervention arms. This binary primary endpoint was used to power the study.

The MARINER trial reported a 2% event rate for a combined outcome of VTE, MI, CVA, or CV deaths in the placebo group (Spyropoulos, 2018). These rates are expected to be higher in COVID-19 patients who are discharged from the hospital. Recent information from patients discharged alive from the University of Pittsburgh Medical Center suggests that the 30-day mortality rate in this population could be as high as 4%. To be conservative, 4% was used as the expected CE rate of events for the no anticoagulant arm. An effect size of 35% percent risk reduction (risk ratio = 0.65) in the anticoagulant group compared to the no anticoagulant group was used to calculate the expected sample size for the study.

The analysis will use a group-sequential two-sample two-sided Z-test for proportions with pooled standard deviation to test the primary hypothesis at overall significance two-sided level alpha = 0.05. Four equally spaced interim analyses and one final analysis will use O'Brien-Fleming alpha spending boundaries for efficacy and the Hwang-Shih-DeCani boundaries for the futility reviews (O'Brien and Fleming, 1979; Hwang, Shih, and De Cani, 1990). In order to ensure an 80% power to detect a CE rate reduction of 35% through anticoagulation use, the study needs to enroll at least 2,530 participants per arm. Since the primary outcome is observed within 30 days of follow-up, the loss to follow-up and withdrawal of consent rates should be low, and it is estimated that CE will be missing on a maximum of 5% of the participants. Therefore, the sample size required for this study will be approximately 2,660 per

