### 3.7.2 INTERIM ANALYSES FOR FUTILITY AND EFFICACY REVIEW

The trial design planned for 4 interim analyses and a final analysis at equally-spaced information points. At each interim analysis cumulative primary outcome data, and potentially the secondary analyses, will be presented to the DSMB. Based on the data, a decision to stop or continue the trial will be taken following the O'Brien-Fleming Rule. If the Z-statistic crosses the lower boundary, the trial will be stopped for futility while if the Z-statistic crosses the upper boundary, the trial will be stopped declaring anticoagulant to be effective in preventing CE. In either case, Stage 1 of the trial will end and secondary analyses, including subgroup analyses will be critical for driving adaptive changes made based on accrued data. Eligibility criteria, efficacy, and safety endpoints will be analyzed at predefined intervals to guide the design of subsequent stages to allow efficient use of data and resources to inform the adaptations in trial design.

Assessments of futility will be conducted at all interim looks, whereas efficacy will only be assessed starting at the third interim analysis (after 60% of the information accumulated; **Table 1**). For the efficacy and futility, O'Brien-Fleming analog alpha-spending function and Hwang-Shih-DeCani beta-spending function will be utilized to create the non-binding boundaries. **Table 1** and **Figure 2** provide specific efficacy and futility boundaries at each interim analysis.

**Table 1:** Stopping Boundaries for Efficacy and Futility based on Z-statistic above.

Look	Information fraction	Efficacy Boundary	Futility Boundary
1	20%	NA	0.1383
2	40%	NA	-0.5933
3	60%	-2.6686	-1.1439
4	80%	-2.2887	-1.5918
Final	100%	-2.0307	-2.0307

**Figure 2:** Stopping Boundaries for Efficacy and Futility based on the Z-statistic described above.

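### The fallback levels for the key secondary endpoints take no account of the look at which CE30 stops the trial, so their benefit-direction error is not held at half the stated level; the SAP 3.2 gate wording also needs tightening.

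*SAP*

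**What the plan says.** SAP 3.5 sets up a group-sequential test of CE30 to "test the primary hypothesis at overall significance two-sided level alpha = 0.05". Under SAP 3.7.2, efficacy is assessed at 60%, 80% and 100% information, with boundaries of magnitude 2.6686, 2.2887 and 2.0307. On an efficacy crossing "the trial will be stopped declaring anticoagulant to be effective in preventing CE", Stage 1 ends and the secondary analyses follow.

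SAP 4.3 and Protocol A5.5 test six ordered secondaries once CE30 is rejected: QOL&M30, QOL&M90, CE45, CE90, CEVTE30, CEATE30. "Using a fallback method the 0.05 type I error rate would be split as follows": 0.025 for the first and 0.005 for each of the others, with the level of a rejected endpoint passed to the next. QOL&M30 and QOL&M90 use a proportional odds model. The other four follow SAP 4.2, which contains a fixed Z-test and no boundaries. The only boundaries in either document are those for CE30.

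SAP 3.2 words the gate differently: secondaries are formally tested "only if the primary endpoint was statistically significant at the two-sided 5% level". Protocol 4.2.2 uses the same criterion. SAP 1.0 adds a general assurance: "Proper statistical approaches are used to control type I error at the interim and final analyses".

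**The concern.** The look at which the secondaries are tested is chosen by CE30, and several of them are built from it. CE45 and CE90 contain every CE30 event; CEVTE30 and CEATE30 are parts of it. An early stop happens when CE30 looks unusually good, and a correlated secondary then tends to look good by chance as well. A gate on a group-sequential primary does not by itself correct for this if the secondary is tested at the same level at every look.

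Early stopping is likely under the design assumptions (see the working), so a rule is needed. At stake is a false claim of benefit on a secondary after an early stop, presented as held at half its level when it is not.

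The gate wording raises a second, smaller issue. CE30 can reach nominal two-sided 5% at the final look without crossing its boundary, so SAP 3.2 and SAP 3.7.2 can give different answers on whether the family opens.

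**Working it through.** **Inputs from the documents.** Looks: "The trial design planned for 4 interim analyses and a final analysis at equally-spaced information points" (SAP 3.7.2). First efficacy look: "efficacy will only be assessed starting at the third interim analysis". Futility: the spending functions "will be utilized to create the non-binding boundaries", so futility stopping is ignored for error control. Design: 4% against 2.6% (risk ratio 0.65), 2,530 evaluable per arm (SAP 3.5). Boundaries are used as magnitudes in the direction of benefit.

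**Assumptions.** The fallback levels are two-sided, like the primary test. Each secondary is tested once, at its full level, at the look where CE30 first crosses. Its information fraction equals that of CE30. The correlation ρ with CE30 is not in the documents, so a range of 0.3 to 0.9 is shown.

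**Step 1: reproduce the plan's boundaries.** O'Brien-Fleming-type spending at one-sided 0.025 is α(t) = 2[1 − Φ(z/√t)], with z = Φ⁻¹(1 − 0.025/2). It gives cumulative 0.0038, 0.0122 and 0.0250 at t = 0.6, 0.8 and 1. The resulting boundaries are 2.6686, 2.2887 and 2.0307, as printed. Their nominal two-sided p-values are 0.0076, 0.0221 and 0.0423.

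**Step 2: how likely is an early stop?** The expected final Z (drift) is d = 0.014 / √(2 × 0.033 × 0.967 / 2,530) = 2.79. The printed boundaries then give a probability of 0.31 of an efficacy stop at 60% and 0.28 at 80%.

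**Step 3: benefit-direction error of a true-null secondary.** For two-sided level a, put c = Φ⁻¹(1 − a/2). With f_k the density of CE30's Z at look k among trials not yet stopped for efficacy, and b_k its boundary,

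E = Σ_k ∫_{z ≥ b_k} f_k(z) · {1 − Φ[(c − ρ(z − d√t_k)) / √(1 − ρ²)]} dz.

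Maximising over the CE30 drift d:

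| Level a | Half level | ρ = 0.3 | ρ = 0.5 | ρ = 0.7 | ρ = 0.9 |
|---|---|---|---|---|---|
| 0.005 | 0.0025 | ×1.04 | ×1.10 | ×1.20 | ×1.4 (about 0.0035) |
| 0.025 | 0.0125 | ×1.04 | ×1.08 | ×1.17 | ×1.36 |
| 0.035 | 0.0175 | ×1.03 | ×1.08 | ×1.16 | ×1.34 (0.0234) |
| 0.05 | 0.0250 | ×1.03 | ×1.08 | ×1.15 | ×1.32 (0.0330) |

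At ρ = 0.9 the maxima for levels 0.025 to 0.05 lie at a drift of about 1, where CE30 crosses in roughly 12% to 19% of trials. For level 0.005 the maximum lies near zero drift. At the planned drift of 2.79 the largest ratio is 0.0270/0.0250 = 1.08 (level 0.05, ρ = 0.7); at ρ = 0.9 it is about 1.02 or less.

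**Step 4: two-sided error.** Adding the harm tail, no drift (−1 to 8) or correlation (0 to 0.999) takes the total above the level. At level 0.05 the maximum is 0.0500. A gate that opens only on benefit nearly empties the harm tail, which offsets the gain on the other side.

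**Step 5: the gate.** Under the CE30 null, the probability of crossing at 60% or 80% is 0.0122. Adding a final Z above 2.0307 brings the total to 0.0250; adding a final Z above 1.96 instead brings it to 0.0283.

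**The case against.** The plan states its error rate on the two-sided scale, and step 4 shows that each level holds there. A reader might infer from the missing boundaries that the type I error control in SAP 1.0 and 4.3 fails after an early stop; the documents do not support that. What remains is one-directional. The efficacy boundaries lie on one side only and the SAP's secondary questions ask whether apixaban reduces or improves the outcome, so false benefit is the error of interest. Half the level is the usual standard for it, though the SAP does not state that standard for the secondaries.

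Full-level testing at the stopping look is inferred from silence. That stands as a limit on confidence, but it is also the gap: a fixed split with no rule by look gives the analyst no other instruction.

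The larger ratios need particular conditions. CE45 reaches 0.035 only if QOL&M30 and QOL&M90 are both rejected (0.025 + 0.005 + 0.005). CE45 must also be truly null while CE30, which it contains, has a weak effect. QOL&M30, which holds half the alpha, shares only mortality with CE30; at an assumed ρ of 0.2 to 0.3 its excess is about 2% to 4%. CE45 and CE90 also mature after CE30, so their information at the stop may differ from what is assumed here. All of this stands.

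On the gate, a reader might infer that the plan allows secondary claims after an unrejected CE30, or after a result against apixaban. SAP 3.2 refers to SAP 4.3, which requires rejection of the primary hypothesis. SAP 3.5 makes 0.05 the overall level, and SAP 3.7.2 declares efficacy only in favour of the anticoagulant. Read together, a final Z of 2.00 is not a rejection. The defect is in the literal wording.

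**Conclusion.** The concern holds in a limited form. The plan does not say how the fallback levels apply when CE30 stops the trial early, and under the natural reading benefit-direction error is not assured at half the level for secondaries correlated with CE30. CE45 and CE90 are the main exposure. The excess is at worst about 15% to 20% at ρ = 0.7 and 30% to 40% at ρ = 0.9, with a weak CE30 effect; about 3% to 10% at ρ = 0.3 to 0.5; and at most about 8% at the planned effect. Two-sided error is within every stated level.

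The gate wording in SAP 3.2 and Protocol 4.2.2 conflicts with the final boundary for Z between 1.96 and 2.0307. Taken literally this costs 0.0033 of one-sided error (0.0283 − 0.0250).

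Both points deserve correction; neither undermines the primary analysis. Confidence is moderate, because the correlations, the equal information fractions and full-level testing at the stop are assumed.

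**What to change.** **1. SAP 4.3 and Protocol A5.5.** State a spending function for each key secondary at the fallback level it holds when tested, over the 60%, 80% and 100% looks. Test it once, against that boundary, at the look where CE30 crosses. State also which data are used for CE45, CE90 and QOL&M90 at an early stop. Two-sided thresholds at 60/80/100% are:

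| Level | O'Brien-Fleming-type | Pocock-type |
|---|---|---|
| 0.025 | 0.0025 / 0.0097 / 0.0217 | 0.0177 / 0.0096 / 0.0088 |
| 0.005 | 0.0002 / 0.0014 / 0.0045 | 0.0035 / 0.0017 / 0.0015 |

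Either holds worst-case benefit-direction error below half the level: at level 0.025, 0.0112 (O'Brien-Fleming-type) or 0.0109 (Pocock-type) against 0.0125.

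The costs fall in different places. Take a secondary with 80% power at a fixed 0.025, so an expected final Z of 2.241 + 0.842 = 3.083. At the final look its power is Φ(3.083 − 2.296) = 78% with O'Brien-Fleming-type spending and Φ(3.083 − 2.621) = 68% with Pocock-type. At a 60% stop the expected Z is 3.083 × √0.6 = 2.388. Ignoring the correlation with CE30, power is 56% at the full level (2.388 − 2.241), 26% with O'Brien-Fleming-type (2.388 − 3.020) and 51% with Pocock-type (2.388 − 2.372). The sponsor should choose with these costs stated.

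**2. SAP 3.2 and Protocol 4.2.2.** Replace the 5% criterion with: *only if CE30 has crossed its efficacy boundary in favour of apixaban*. This changes wording only and matches SAP 3.7.2.

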Appendix 5. Addition of New Key Secondary and Exploratory Outcomes

A5.1 Rationale for new Secondary and Exploratory Outcomes

Health-related quality of life data has been collected on participants in ACTIV 4c by use of the EuroQol 5 Dimension 5 Level (EQ-5D-5L) survey, administered at three timepoints following randomization into the study: Day 2 (within the first few days of starting study drug), Day 30 (time of completion of study drug), and Day 90 (60 days after completion of study drug). The EQ-5D survey consists of five questions that cover the following domains: mobility, self-care, usual activities, pain/discomfort, and anxiety/depression. The response to each question is collected as a 5-level ordinal scale, spanning scores of 1 (no problems, or best outcome), 2 (slight problems), 3 (moderate problems), 4 (severe problems) and 5 (extreme problems, or worst outcome). The rationale for collecting these quality of life data was driven by early reports describing a significant subset of patients with COVID-19 who had a prolonged course with persistent symptoms of fatigue, dyspnea, and other problems, lasting for months and longer after the acute illness.

An analysis of the EQ-5D data was not included in the Master Protocol, since study leadership had not anticipated that anticoagulant therapy would have a significant impact on quality of life. A post-hoc analysis of EQ-5D data collected in ACTIV 4a, however, comparing prophylactic-dose with therapeutic-dose anticoagulation in hospitalized patients with COVID-19 in the non-ICU setting, observed that patients randomized to therapeutic anticoagulation had less moderate-to-extreme impairment scores in four of the five EQ-5D domains at 90 days after hospital discharge. This difference was statistically significant in the self-care domain, with an improvement from 8.4% to 2.9% of participants having moderate-to-extreme impairment scores with therapeutic anticoagulation, for an odds ratio (adjusted for age, co-morbidities and pre-hospitalization status) of 0.26 (95% CI, 0.08-0.83) and a p-value of 0.016 ([name] and [name], personal communication). This preliminary observation that anticoagulant therapy could impact quality of life in patients with COVID-19 resulted in the decision by the ACTIV 4c leadership team to include an analysis of the collected EQ-5D data in two new secondary objectives and one new exploratory objective.

A5.2 New Secondary Objectives

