## B. BASELINE CHARACTERISTICS

Table: Baseline characteristics of randomized participants

	Randomized	Arm A	Arm B
	N=	N=	N=
Stratification			
Antiplatelet Use (%)			
Hospitalization Severity (%)			
Severe			
Moderate			
Demographics			
Age (median (q1,q3)) 			
Biological sex = Female (%)			
Race (%)			
White			
Asian			
Black or African American			
American Indian or Alaska Native			
Native Hawaiian or other Pacific Islander			
Aboriginal or First Nations			
Middle Eastern or North African			
More than one race			
Other race			
Unknown			
Ethnicity (%)			
Hispanic or Latino			
Not Hispanic or Latino			
Unknown			
Medical History			
Cardiovascular			
Hypertension (%)			
Heart Failure			
Coronary Artery Disease (CAD)			
Peripheral Arterial Disease (PAD)			
Cerebrovascular Disease (stroke or TIA)			
Atrial fibrillation / flutter			
Deep Vein Thrombosis (DVT)			
Pulmonary Embolism (PE)			
Known thrombophilia			
Lower limb paralysis / paresis			
History of smoking and/or vaping			
None of the above			
Metabolic, Renal, or Digestive (%)			

Diabetes Type 1			
Diabetes Type 2			
Chronic Kidney Disease			
Liver Disease			
None of the above			
Respiratory (%)			
Asthma			
Chronic Obstructive Pulmonary Disease			
Interstitial Lung Disease			
Pulmonary Hypertension			
History of oxygen use prior to hospitalization			
None of the above			
Immunosuppressive Disease			
HIV/AIDS			
Metastatic Cancer			
Malignancy, receiving chemotherapy or immunotherapy			
History of cancer but not currently in treatment			
Leukemia			
Lymphoma			
Solid organ transplant			
Bone marrow transplant			
Autoimmune disease			
None of the above			
History of seizures			
History of alcoholism			
Current			
Former			
Never			
Unknown			
Baseline Medications			
Hydroxychloroquine / Chloroquine			
Colchicine			
Remdesivir			
IL6 Inhibitors			
Lopinavir / Ritonavir			
Interferon Beta-1a			
Convalescent Plasma			
Dexamethasone			
Azithromycin			
Other steroids (not Dexamethasone)			
Monoclonal Antibody			
Anticoagulants			
Anti-platelets			

IV argatroban continuous infusion			
IV argatroban continuous infusion			
IV bivalirudin continuous infusion			
IV unfractionated heparin infusion			
Unfractionated heparin subcutaneous			
Acenocoumarol			
Apixaban			
Dabigatran			
Dalteparin			
Edoxaban			
Enoxaparin			
Fluindione			
Fondaparinux			
Nadroparin			
Phenprocoumon			
Rivaroxaban			
Tinzaparin			

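### The tested models for QOL&M30 and QOL&M90 omit baseline comorbidity: a modest efficiency loss that is cheap to avoid

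*SAP*

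**What the plan says.** SAP 4.3 and Protocol A5.5 give the same model for QOL&M30 and QOL&M90: "The covariates in the model will include the participant's age (restricted cubic spline with 3 knots), sex, D-dimer (normal or abnormal), BMI". BMI also enters as a spline, and antiplatelet use at enrolment, dichotomised WHO severity and treatment complete the list. There is no comorbidity term and no term for status before admission.

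Protocol A5.1 says that EQ-5D was "administered at three timepoints following randomization into the study: Day 2", then at Days 30 and 90. Day 2 falls just after study drug has started. The same section describes the result that motivated these endpoints, from an inpatient trial in the same programme, as adjusted: "for an odds ratio (adjusted for age, co-morbidities and pre-hospitalization status) of 0.26".

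The baseline table in SAP Appendix 3, part B, lists cardiovascular, metabolic/renal/digestive, respiratory and immunosuppressive history. The respiratory block includes "Chronic Obstructive Pulmonary Disease" and also "History of oxygen use prior to hospitalization". Protocol 7.6.3 confirms that clinical history is collected at baseline.

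The secondary analysis of these endpoints is multiple imputation: "20 datasets will be imputed using predictive mean matching and the above covariates plus the Day 2 and Day 90 EQ5D index scores". The estimand table in SAP 3.2 expects about 20% of EQ-5D data to be missing.

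QOL&M30 comes first in the fallback order, with 0.025 of the 0.05. The secondary endpoints are tested only if CE30 is rejected. If the study stops without crossing either CE30 boundary, they are reported as estimates with 95% intervals and no p-values.

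**The concern.** With no EQ-5D value from before randomisation, the strongest usual covariate for a quality-of-life outcome is unavailable, and other baseline predictors have to carry the adjustment. Chronic illness is an obvious candidate. It was used in the motivating analysis and appears in this trial's own baseline table, yet the tested model leaves it out without giving a reason.

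In a proportional odds model, omitting a prognostic covariate moves the treatment odds ratio towards 1 and lowers the test statistic, even when the arms are balanced. QOL&M30 carries half of the secondary alpha, and passing it raises the level for QOL&M90 from 0.005 to 0.03. The SAP also expects little information from secondary endpoints 3 to 6 if CE30 events are scarce, which leaves the two EQ-5D composites as the main efficacy information.

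A lesser point concerns missing data. Comorbidity may also predict which survivors do not return an EQ-5D. Missing at random would be somewhat more credible if the model and the imputation conditioned on it.

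**Working it through.** **The plan's own figures.** No power or sample size is stated for QOL&M30 or QOL&M90. The figures that bear on them reproduce:
- CE30 sample size, 4% against 2.6% (4% × 0.65), two-sided 0.05, 80% power, pooled Z-test: [1.960 × √(2 × 0.033 × 0.967) + 0.8416 × √(0.04 × 0.96 + 0.026 × 0.974)]² / 0.014² = 2,555 per arm, against 2,530 stated (1% apart).
- 2,530 / 0.95 ≈ 2,663, against about 2,660 stated.
- Fallback split: 0.025 + 5 × 0.005 = 0.05, and 0.025 + 0.005 = 0.03.
- Participants with EQ-5D: 0.80 × 2,660 = 2,128 per arm.

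**Approximate gain from adding the terms.** Let ρ be the partial correlation of the added terms with the outcome, given the covariates already in the model. This is an assumption, since the documents give none. Treating the gain as a residual-variance cut of 1 − ρ², and assuming 80% power now at two-sided 0.025:

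Power = Φ[(2.2414 + 0.8416)/√(1 − ρ²) − 2.2414]

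| ρ | 3.0830/√(1 − ρ²) | Power | Gain (points) |
|---|---|---|---|
| 0.2 | 3.147 | 81.7% | 1.7 |
| 0.3 | 3.232 | 83.9% | 3.9 |
| 0.35 | 3.291 | 85.3% | 5.3 |
| 0.4 | 3.364 | 86.9% | 6.9 |
| 0.5 | 3.560 | 90.6% | 10.6 |

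**Check by simulating proportional odds models.** Assumptions: 2,128 per arm, seven ordered levels, 2% deaths, 250 runs per scenario, and one modelled covariate explaining 10% of latent variance. Mean Z without and with the extra covariate was 3.06/3.16, 3.01/3.17, 3.01/3.32 and 2.95/3.43 at ρ = 0.2, 0.3, 0.4 and 0.5. Scaling 3.0830 by each ratio gives about 83%, 84%, 88% and 91%, in line with the formula.

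**The same question as a loss.** A second simulation assumed eight levels, 2.5% deaths, 35% at the ceiling, a conditional odds ratio of 1.25, 2,128 per arm and 60 runs. R² is the share of latent variance explained by the extra covariate.

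| R² | Odds ratio omitted / included | Mean Z omitted / included | Power if omitted, when the fuller model has 80% | Gain as extra patients, (Z ratio)² − 1 |
|---|---|---|---|---|
| 2% | 1.255 / 1.258 | 4.135 / 4.176 | 79% | 2% |
| 5% | 1.247 / 1.257 | 4.031 / 4.149 | 77–78% | 6% |
| 10% | 1.240 / 1.259 | 3.922 / 4.156 | 75% | 12% |
| 20% | 1.221 / 1.259 | 3.637 / 4.106 | 69% | 28% |

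**How the gain appears.** The approximate standard error of the log odds ratio is ln(OR)/Z. At R² = 10% it is ln(1.240)/3.922 = 0.0548 with the covariate omitted and ln(1.259)/4.156 = 0.0554 with it included. The interval does not narrow. The estimate moves away from 1 by more than its standard error grows.

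**The case against.** The model already has six prespecified baseline covariates, including both stratification factors and splines for age and BMI. What comorbidity adds beyond these may be small. Under the formula the gain reaches 5 points only at ρ of about 0.35 or more, and nothing in the documents shows that a crude count and one binary item would reach that. If the true odds ratio were 1.25 with 2,128 per arm, power would be about 97% with the covariate and still 95% to 97% without it at R² up to 10%. This stands and sets the priority.

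The gate also stands. Formal testing follows only a CE30 success. In the low-event case no p-value is given, so the 0.025 and any power figure fall away.

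The missing-data argument is weakened because the imputation already uses EQ-5D from other visits, plausibly a better predictor than a comorbidity count. As written, though, only Day 2 adds information when the outcome is Day 90. That comorbidity drives non-response is plausible but not documented.

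The motivating analysis sets no standard. It was post hoc, in another trial, on dichotomised single domains, and its covariate definitions are not given. It shows only that comorbidity was thought relevant.

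What remains is that the data appear to be in hand and the change is small. No scenario examined showed a loss from adding a prognostic term.

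**Conclusion.** The point holds as an optional efficiency gain; priority: consider. The size is about 2, 4 or 7 power points at ρ of 0.2, 0.3 or 0.4. It rests on an assumed 80% starting power and an assumed correlation, and counts as power only after CE30 is rejected.

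Three stronger readings are tempting, and the documents do not support them:
- **That the omission biases the test or inflates type I error.** It does not. The odds ratio nearer 1 reflects non-collapsibility, and under no effect both models target an odds ratio of 1.
- **That the trial records pre-hospital function and ignores it.** The only explicit item on status before admission is prior oxygen use, in a table shell for the monitoring board rather than the case report form. Other items are neither shown nor excluded.
- **That a model change can make up for the missing baseline EQ-5D.** It cannot. That is a limit of data collection, and Day 2 EQ-5D is measured after randomisation, so it is no substitute in the tested model.

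**What to change.** In SAP 4.3 and Protocol A5.5, add two prespecified baseline covariates to the current list for QOL&M30 and QOL&M90:
1. A comorbidity count from 0 to 4: the number of baseline-table categories (cardiovascular; metabolic, renal or digestive; respiratory; immunosuppressive) with at least one condition. Leave the oxygen item out of the respiratory category so that it is not counted twice, and state whether the smoking/vaping entry in the cardiovascular block counts.
2. Oxygen use before hospitalisation (yes/no).

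Add a simple rule for missing baseline items, identical in both arms. Because the imputation reuses the model's covariates, both terms enter it without further change. Keep Day 2 EQ-5D out of the tested model, and state that no EQ-5D value from before randomisation exists.

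Under SAP 1.0, once unblinded review has begun, the blinded statisticians must make this edit. It needs no new data collection if the case report form matches the table shell. It costs two degrees of freedom, a short definition of the count, and an odds ratio conditional on two more covariates.
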